3 OBJECTIVES AND ENDPOINTS

3.1 Objectives, Hypotheses, and Estimands

Primary

The primary objective of the study is to assess the efficacy, safety, and tolerability of ABBV-154 in comparison with placebo in subjects with moderately to severely active CD who had inadequate response to or were intolerant of prior biologics.

- **Primary Efficacy Objective:** The primary efficacy objective of the study is to demonstrate a higher rate of endoscopic response after 12 weeks of treatment with ABBV-154 when compared to placebo in subjects with moderately to severely active CD who had inadequate response to or were intolerant of prior biologics.

The hypothesis corresponding to the primary efficacy objective is the proportion of subjects achieving endoscopic response with ABBV-154 is greater than that with placebo at Week 12. The estimand for the primary endpoint is defined as the difference in the proportion of subjects that achieve endoscopic response at Week 12 without use of concomitant medication that could confound the efficacy (see Section 7.3) and regardless of premature discontinuation of study drug, in each of the ABBV-154 dose groups compared with the placebo group in subjects with moderately to severely active CD who had inadequate response to or were intolerant of prior biologics.

- **Secondary Efficacy Objectives:** The secondary efficacy objectives of the study are to demonstrate greater efficacy with ABBV-154 treatment when compared with placebo treatment with respect to the secondary endpoints specified in Section 3.3, in subjects with moderately to severely active CD who had inadequate response to or were intolerant of prior biologics.
- The estimands corresponding to the secondary efficacy endpoints are as follows:
 - For endpoints in the Induction Period: The difference in the proportion of subjects that achieve a response without use of concomitant medication that could confound the efficacy (see Section 7.3) and regardless of premature discontinuation of study drug, in each of the ABBV-154 dose groups compared with the placebo group in subjects with moderately to severely active CD who had inadequate response to or were intolerant of prior biologics.
 - For endpoints in the Maintenance Period: The difference in the proportion of subjects that achieve a response without use of concomitant medication that could confound the efficacy (see Section 7.3) and regardless of premature discontinuation of study drug, in each of the ABBV-154 dose groups compared with the placebo group in subjects with moderately to severely active CD who had inadequate response to or were intolerant of prior biologics and achieved response after the 12-week induction treatment with ABBV-154.

Secondary Objectives

The secondary objectives are to assess the pharmacokinetics (PK), pharmacodynamics (PD), and immunogenicity of ABBV-154.

3.2 Primary Endpoint

The primary endpoint is the achievement of endoscopic response at Week 12 in the Induction Period defined as a decrease in Simple Endoscopic Score for Crohn's Disease (SES-CD¹⁷) > 50% from Baseline (or for subjects with isolated ileal disease and a Baseline SES-CD of 4, at least a 2-point reduction from Baseline).

3.3 Secondary Endpoint(s)

Secondary Endpoint(s)

- Achievement of clinical remission per Crohn's Disease Activity Index (CDAI) at Week 12 in the Induction Period defined as CDAI < 150.
- Achievement of clinical remission per average daily liquid or very soft stool frequency (SF) and average daily abdominal pain (AP) score (SF/AP) at Week 12 in the Induction Period defined as average daily liquid or very soft SF ≤ 2.8 and not worse than Baseline AND average daily AP score ≤ 1 and not worse than Baseline.
- Achievement of endoscopic response per SES-CD at Week 40 in the Maintenance Period.
- Achievement of clinical remission per CDAI at Week 40 in the Maintenance Period.
- Achievement of clinical remission per SF/AP at Week 40 in the Maintenance Period.

3.4 Additional Efficacy Endpoints

In the Induction/Re-Induction/Maintenance Periods, the additional endpoints below will be analyzed at timepoints specified in the schedule of events table of the protocol (in this section, "Baseline" refers to the Baseline [Week 0, Day 1] of the Induction Period):

- Achievement of clinical remission per CDAI.
- Achievement of clinical remission per SF/AP.
- Achievement of clinical response defined as a decrease of CDAI ≥ 100 points from Baseline (CR100).
- Achievement of clinical response per SF/AP defined as ≥ 30% decrease in average daily liquid or very soft SF and/or ≥ 30% decrease in average daily AP score and both not worse than Baseline.
- Achievement of enhanced clinical response per SF/AP defined as ≥ 60% decrease in average daily liquid or very soft SF and/or ≥ 35% decrease in average daily AP score and both not worse than Baseline, and/or clinical remission per SF/AP.

- Achievement of endoscopic remission defined as SES-CD \leq 4 and at least a 2-point reduction versus Baseline and no subscore $>$ 1 in any individual variable.
- Change from Baseline in Inflammatory Bowel Disease Questionnaire (IBDQ^{18,19}) total score.
- Change from Baseline in Functional Assessment of Chronic Illness Therapy-Fatigue (FACIT-F²⁰).
- Change from Baseline in the Bowel Incontinence Scale.
- Change from Baseline in CDAI.
- Change from Baseline in individual IBDQ domain scores (bowel, emotional, social, systemic).
- Change from Baseline in individual IBDQ items under Bowel Symptom domain (for Q1, Q5, Q9, Q13, Q17, Q20, Q22, Q24, Q26, and Q29).
- Achievement of IBDQ remission defined as IBDQ \geq 170 points.
- Achievement of IBDQ response defined as increase in IBDQ \geq 16 points from Baseline.
- Change from Baseline in 36-Item Short Form Health Survey (SF-36^{21,22}).
- Change from Baseline in fecal calprotectin (FCP).
- Change from Baseline in high-sensitivity C-Reactive Protein (hs-CRP).
- Change from Baseline in average daily AP score.
- Change from Baseline in average daily liquid or very soft SF.
- Change from Baseline in SES-CD.
- Achievement of SES-CD ulcerated surface subscore \leq 1 in each segment in subjects with a SES-CD ulcerated surface subscore \geq 2 at Baseline.
- Achievement of ulcer-free endoscopy: SES-CD ulcerated surface subscore of 0 in subjects with SES-CD ulcerated surface subscore \geq 1 at Baseline.
- Change from Baseline in daily physical activity for subjects participating in the Wearable Device Substudy.
- Change from Baseline in sleep parameters for subjects participating in the Wearable Device Substudy.
- Change from Baseline in stool frequency, as captured from the wearable device, for subjects participating in the Wearable Device Substudy.
- Patient Global Impression of Change – Crohn's Disease+ (PGIC-CD+).
- Change from Baseline in Patient Global Impression of Severity – Crohn's Disease+ (PGIS-CD+).
- Achievement of absence of bowel urgency.
- Change from Baseline in average daily bowel urgency frequency.
- Achievement of absence of rectal bleeding.

All endoscopic endpoints will be scored by a central reviewer.

SF/AP-based efficacy endpoints will be analyzed in the subset of subjects with an average daily liquid or very soft SF score ≥ 4 and/or average daily AP score ≥ 2 at Baseline.

3.5 Safety Measures

- Treatment emergent adverse events (TEAEs), serious adverse events (SAEs), AEs leading to discontinuation of the study drug;
- Occurrence of possible glucocorticoid-related AEs;
- Potentially clinically significant laboratory, vital signs, and electrocardiogram (ECG) variables.

3.6 Pharmacokinetic Endpoints

Serum or plasma concentrations of the conjugated ADC, total antibody, free payload A-1677770 will be determined at Baseline (pre-dose) of the Induction Period and at timepoints during the treatment period as specified in the Activity Schedule ([Appendix D](#)).

Development of anti-drug antibody (ADA) to ABBV-154 will be evaluated and if confirmed positive, titers will be measured. Samples that are confirmed positive may be further characterized in a validated neutralizing antibody (nAb) assay. Immunogenicity samples will be collected at Baseline (pre-dose) of the Induction Period and at timepoints as specified in the Activity Schedule ([Appendix D](#)).

3.7 Exploratory Biomarker Research

The effect of the ADC compound on glucocorticoid-related endpoints will be assessed by blood samples and intestinal tissue biopsies collected throughout the study at timepoints as specified in the Activity Schedule ([Appendix D](#)). The biomarkers to be analyzed include, but are not limited to the following:

- Neuroendocrine biomarkers (total and free cortisol and adrenocorticotrophic hormone [ACTH])
- Bone formation (osteocalcin, procollagen type 1 N-propeptide [P1NP]), and bone resorption (C-terminal telopeptide of type I [CTX-I]) biomarkers
- Biopsy tissue only - Histological, proteomic, or genomic biomarkers (may include but not limited to glucocorticoid-related genes and proteins).

Provision of these biospecimens for biomarker research is mandatory, but they will not be collected from sites where local regulations do not allow for the collection, use, and storage of samples described in the protocol.

Additional optional biospecimens (whole blood for serum, plasma, peripheral blood mononuclear cells [PBMC], RNA, and DNA) will be collected throughout the study at timepoints as specified in the Activity Schedule ([Appendix D](#)) to evaluate known and/or novel disease-related or drug-related biomarkers in circulation. Types of biomarkers may include nucleic acids, proteins, cell populations, lipids, and/or metabolites, either free or in association with particular cell types. The analyses may include but are not limited to soluble proteins, genomic transcripts, blood leukocyte populations, and genetic analysis to

evaluate biomarker endpoints related to safety, disease state, and target pathway. Results from this optional biomarker research results may not be included in the clinical study report. Further details regarding the biomarker research rationale and collection time points are provided in the Operations Manual, [Appendix F](#), Section 3.21.

4 INVESTIGATIONAL PLAN

4.1 Overall Study Design and Plan

This is a randomized, double-blind, placebo-controlled Phase 2b study to assess the safety, tolerability, PK, PD, immunogenicity, and efficacy of ABBV-154 in subjects with moderately to severely active CD who had inadequate response to or were intolerant of prior biologics. The enrollment for subjects with prior adalimumab use is capped at approximately 30% of the total enrolled subjects. The study comprises 3 periods: a 12-Week Double-Blind Placebo-Controlled Induction Period, a 12-Week Double-Blind Re-Induction Period (for subjects considered to be clinical non-responders and endoscopic non-responders), and a 40-Week Double-Blind Placebo-Controlled Maintenance Period.

At the Baseline Visit of the Induction Period, approximately 265 subjects will be randomized in a 1:1:1:1:1 ratio into 4 ABBV-154 treatment groups or placebo:

1. Induction Group 1: Loading dose of 150 mg IV at Week 0, followed by 80 mg subcutaneous (SC) at Week 2 and every other week (EOW);
2. Induction Group 2: Loading dose of 300 mg IV at Week 0, followed by 230 mg SC at Week 2 and EOW;
3. Induction Group 3: Loading dose of 600 mg IV at Week 0, followed by 530 mg SC at Week 2 and EOW;
4. Induction Group 4: Loading dose of 600 mg IV at Week 0, followed by 530 mg SC at Weeks 4 and 8, and placebo at Weeks 2, 6, and 10; and
5. Induction Group 5: Matching placebo (IV and SC).

At Week 12 of the Induction Period, subjects achieving clinical response, defined as a decrease in CDAI ≥ 100 points from Baseline (CR100) AND/OR endoscopic response (per local read) will receive treatment in the 40-Week Maintenance Period as follows:

1. Induction Group 1: Re-randomized in a 1:1 ratio to receive ABBV-154 80 mg SC EOW or matching placebo;
2. Induction Groups 2 to 4: Re-randomized in a 1:1:1 ratio to receive ABBV-154 80 mg SC EOW, ABBV-154 230 mg SC EOW, or matching placebo;
3. Induction Group 5: ABBV-154 80 mg SC EOW.

At Week 12 of the Induction Period, subjects who are categorized as clinical non-responders and endoscopic non-responders (per local read) will be re-randomized into the Re-Induction Period.

Subjects who demonstrate inadequate response at or after Week 8 in the Induction Period may receive Rescue Therapy with oral glucocorticoids as defined in Section 5.4.

Subjects who receive Rescue Therapy, fail to complete glucocorticoid tapering by Week 6, or increase doses of or initiate treatment with aminosaliclates or immunomodulators in the Induction Period will be considered non-responders, regardless of clinical response or endoscopic response (per local read) per the definitions above at Week 12 and will be re-randomized in a 1:1 ratio into 2 ABBV-154 treatment groups in the 12-Week Re-Induction Period as follows:

1. Re-Induction Group 1: Loading dose of 300 mg IV at Week 0, followed by 230 mg SC at Week 2 and EOW;
2. Re-Induction Group 2: Loading dose of 600 mg IV at Week 0, followed by 530 mg SC at Week 2 and EOW.

Subjects who achieve clinical response AND/OR endoscopic response (per local read) at Week 12 of the Re-Induction Period will be re-randomized into the Maintenance Period as described above for subjects achieving clinical response AND/OR endoscopic response (per local read) after Week 12 of the Induction Period. Subjects who do not achieve either clinical response or endoscopic response (per local read) after the Re-Induction Period will be discontinued and will have a follow-up visit scheduled 70 days after last study drug administration.

To determine endoscopic response status for re-randomization into the Maintenance Period, the SES-CD score per local read at Week 12 of the Induction/Re-Induction Period and the SES-CD score per central read at Baseline will be used. In the case of missing data where either clinical response or endoscopic response cannot be determined, subjects will be considered non-responders for the re-randomization criteria evaluation.

Subjects who have an inadequate response at or after Week 4 in the Maintenance Period will be eligible to receive Rescue Therapy with a single dose of ABBV-154 600 mg IV followed by ABBV-154 230 mg SC EOW. Subjects who have received rescue therapy with ABBV-154 for at least 4 weeks and who continue to demonstrate inadequate response may receive additional Rescue Therapy with oral glucocorticoids, aminosaliclates, or immunomodulators. Rescue Therapy options for the Maintenance Period are further described in Section 5.4.

The last dose of study drug will be given at Week 38 of the Maintenance Period. A follow-up visit will be scheduled 70 days after the last study drug administration.

[figure not shown]
The Primary Analysis for the Induction Period and Re-Induction Period will be performed after all subjects have either completed Week 12 of the Induction Period and Re-Induction Period, respectively, or prematurely discontinued study participation. The final analysis will be conducted after all subjects have completed Week 40 of the Maintenance Period plus the 70-day Follow-up Visit or prematurely discontinued study participation. To ensure the integrity of the trial, the study sites and subjects will remain blinded until the final database lock is completed (see Section 7.1).

Interim analyses may be performed as outlined in Section 7.8.

The Wearable Device Substudy will enroll up to approximately 75 subjects in countries and sites where the digital health technology device is deployed and available. For subjects participating in the substudy, data for sleep parameters, daily physical activity, and stool frequency will be collected continuously throughout the Induction Period.

The schematic of the study is shown in [Figure 1](#). Further details regarding study procedures are located in the Operations Manual. See [Section 5.1](#) for information regarding eligibility criteria.

Figure 1. Study Schematic

DB = double-blind; EOW = every other week; IV = intravenous; SC = subcutaneous; Wk = week

* Responders are defined as clinical responders AND/OR endoscopic responders (per local read), and non-responders are defined as clinical non-responders AND endoscopic non-responders (per local read). Clinical responder is defined at Week 12 of the Induction Period or Re-Induction Period as a decrease in CDAI \geq 100 points from Baseline (CR100). Endoscopic responder is defined at Week 12 of the Induction Period or Re-Induction Period as a decrease in SES-CD $>$ 50% from Baseline (or for subjects with isolated ileal disease and a Baseline SES-CD of 4, at least a 2-point reduction from Baseline) (per local read). In the case of missing data where clinical response and endoscopic response cannot be calculated, subjects will be considered as non-responders for the re-randomization criteria evaluation.

** Only subjects who are considered to be clinical non-responders and endoscopic non-responders (per local read) at Week 12 of the Induction Period will be re-randomized into the Re-Induction Period.

*** Subjects with inadequate response at/after Week 4 of the Maintenance Period will be eligible to receive Rescue Therapy consisting of ABBV-154 600 mg IV followed by ABBV-154 230 mg SC EOW.

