Subjects who receive protocol-defined glucocorticoid Rescue Therapy, initiate glucocorticoids (other than inhaled) after Baseline without qualifying for Rescue Therapy, fail to complete glucocorticoid tapering by Week 6, or who increase doses of or initiate treatment with aminosaliculates or immunomodulators during the Induction Period will be considered non-responders and will be re-randomized into the Re-Induction Period. All subjects who fulfill the clinical response AND/OR endoscopic response (per local read) definition at Week 12 of the Re-Induction Period will be re-randomized into the Maintenance Period.

The criteria for inadequate response are the following:

- Induction Period: Presence of clinical symptoms defined as CDAI ≥ 220 and not achieving a decrease in CDAI ≥ 35 points from Baseline of the Induction Period.
- Maintenance Period: Presence of clinical symptoms defined as CDAI ≥ 220 and an increase in CDAI ≥ 70 points from Baseline of the Maintenance Period.
- And, for both the Induction Period and Maintenance Period, presence of at least 1 of the following objective markers of inflammation:
 - hs-CRP \geq ULN, and worse than the lowest value assessed during the study, or
 - FCP ≥ 250 $\mu\text{g/g}$, and worse than the lowest value assessed during the study, or
 - SES-CD, excluding the narrowing component, ≥ 6 (≥ 4 for isolated ileal disease), as scored by the site investigator at an endoscopy.

The last available values for hs-CRP and FCP will be used for assessment of inadequate response.

Use of Rescue Therapy in subjects who qualify is at the investigator's discretion and not mandatory.

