4.0 Analysis Populations

The following population sets will be used for the analyses.

ITT Populations

ITT population: The ITT Population includes all subjects who were randomized and received at least 1 dose of study drug.

ITT1 population: The subset of the ITT Population who were randomized and received at least 1 dose of study drug in the Induction Period. The ITT1 Population is the primary analysis population for efficacy analyses of the Induction Period.

ITT2 population: The subset of the ITT population who were randomized and received at least one dose of study drug in the Re-Induction Period. The ITT2 Population is the analysis population for efficacy analyses of the Re-Induction Period.

ITT3 population: The subset of the ITT population who received ABBV-154 for 12 weeks before entering the Maintenance Period (including subjects were randomized to ABBV-154 dose groups in the Induction Period and entered the Maintenance Period from the Induction Period OR were randomized to the placebo group in the Induction Period and entered the Maintenance Period from the Re-Induction Period) AND were randomized and received at least one dose of study drug in the Maintenance Period. The ITT3 Population is the primary analysis population for efficacy analyses of the Maintenance Period.

ITT3-RN population: The subset of the ITT population who were enrolled and received at least one dose of study drug in the randomized portion of the Maintenance Period.

ITT3-NRN population: The subset of the ITT population who were enrolled and received at least one dose of study drug in the non-randomized portion of the Maintenance Period.

ITT3-RES population: The subset of the ITT population who received at least one dose of ABBV-154 rescue therapy in the Maintenance Period.

The ITT Populations (including ITT1, ITT2, ITT3, ITT3-RN, ITT3-NRN populations) will be analyzed as randomized (i.e., according to the randomized/assigned treatment assignment).

Safety Populations

The safety population for the Induction Period (denoted by **SA1**) includes all subjects who received at least one dose of the study drug in the Induction Period.

The safety population for the Re-Induction Period (denoted by **SA2**) includes all subjects who received at least one dose of the study drug in the Re-Induction Period.

The safety population for the Maintenance Period (denoted by **SA3**) includes all subjects who received at least one dose of the study drug in the Maintenance Period.

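### The Week 12 missing-data routing rule is worded two ways, and the body wording, taken literally, overrides the AND/OR responder definition

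*Protocol*

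**What the plan says.** **Missing-data rule, body text.** The Synopsis (Investigational Plan), Protocol 4.1 and SAP 2.2 make a subject a non-responder for re-randomization "In the case of missing data where either clinical response or endoscopic response cannot be determined".

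**Missing-data rule, figure footnotes.** The single-asterisk footnote to Figure 1, in both Protocol and SAP, does so "In the case of missing data where clinical response and endoscopic response cannot be calculated".

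**Responder rule.** The same footnote states: "Responders are defined as clinical responders AND/OR endoscopic responders (per local read"), with non-responders failing on both. Protocol 4.1 says subjects with clinical response "AND/OR endoscopic response (per local read) will receive treatment in the 40-Week Maintenance Period as follows". The double-asterisk footnote admits only dual non-responders to Re-Induction.

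**After Re-Induction.** Protocol 4.1: "Subjects who do not achieve either clinical response or endoscopic response (per local read) after the Re-Induction Period will be discontinued". Protocol 5.4 re-randomizes into Maintenance "All subjects who fulfill the clinical response AND/OR endoscopic response (per local read) definition at Week 12" of Re-Induction.

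**Analysis sets (SAP 4.0).** ITT3 covers subjects randomized to ABBV-154 in Induction "and entered the Maintenance Period from the Induction Period OR were randomized to the placebo group" and came through Re-Induction. ITT3-RN covers those "who were enrolled and received at least one dose of study drug in the randomized portion of the Maintenance Period".

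**The concern.** One missing-data rule has *either* and the other has *and*. Both stand in current text of both documents, and neither document says which governs.

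The subject who matters has an observed response on one component and no result on the other. Three things depend on the reading:

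- **Treatment.** Under the literal body text, an ABBV-154 Induction responder gets a new load of 300 or 600 mg IV and then 230 or 530 mg SC every other week, instead of re-randomization into Maintenance. A Re-Induction responder is taken off study drug.
- **Analysis sets.** A diverted ABBV-154 Induction responder leaves ITT3. If that subject responds in Re-Induction, they may still enter ITT3-RN, on which SAP 9.4.2 repeats the Maintenance secondary analyses. A diverted placebo responder may enter ITT3 through Re-Induction. Under the AND/OR rule that subject would get 80 mg every other week without randomization and stay outside ITT3.
- **Stratification.** If a subject with a missing CDAI is admitted on endoscopy, neither Protocol 5.8 nor SAP 9.1 states that subject's level of the CR100 stratum.

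**Working it through.** **The plan's own figures.** Inputs from Protocol 7.10 and SAP 2.4: 11% on placebo, a 26-point difference (so 37% on ABBV-154), chi-square test, two-sided alpha 0.1. With the pooled-variance formula and no continuity correction,

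power = Φ{[√n × 0.26 − 1.645 × √(2 × 0.24 × 0.76)] / √(0.11 × 0.89 + 0.37 × 0.63)}.

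- n = 53 per group: 94.1% (stated: more than 90%).
- n = 40 per group: 87.1% (stated: more than 80%).

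Both statements hold, and this point does not challenge them.

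**The rules case by case.** Each component is R (response), N (non-response) or M (missing), giving 3 × 3 = 9 combinations. Four have nothing missing (2 × 2), and all texts agree on those. The other 9 − 4 = 5 are:

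| Clinical / endoscopic | Body text, literal | Footnote with its AND/OR sentence | Component by component |
|---|---|---|---|
| R / M | non-responder | responder | responder |
| M / R | non-responder | responder | responder |
| N / M | non-responder | not covered | non-responder |
| M / N | non-responder | not covered | non-responder |
| M / M | non-responder | non-responder | non-responder |

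- The texts agree in 1 of the 5 and conflict outright in 2 (R/M and M/R).
- In the remaining 2, only the body text gives an answer.
- The component-wise rule decides all 5. It differs from the literal body text only in R/M and M/R, and never from the footnote where the footnote speaks.

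**How many subjects.** The documents give no rate. SAP Appendix B limits missing CDAI: four diary days suffice for the diary items, and hematocrit and weight may come from earlier visits. The other three items must come from the calculation date, and any missing subtotal makes the CDAI missing. There is no similar fallback for a missing endoscopy.

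As an illustration only, assume that a fraction m of the 265 subjects has exactly one component missing at Induction Week 12, and that a fraction r of those respond on the other. The number routed differently is 265 × m × r:

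| m (assumed) | r = 0.3 | r = 0.7 |
|---|---|---|
| 2% | 1.6 | 3.7 |
| 5% | 4.0 | 9.3 |
| 10% | 8.0 | 18.6 |

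**The case against.** The strongest reply is that the body sentence can be read component by component, with a missing component failing only that component. In Protocol 4.1 it directly follows a sentence on how the endoscopic component is determined, and the double-asterisk footnote points the same way. That reading is plausible and would reconcile the texts. But neither document states it, and a programmer could fairly code the literal sentence.

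The opposite reply is that the strict rule may be a deliberate conservative choice, since Protocol 4.1 already overrides observed response for rescue and confounding medication. That override, however, says expressly that it applies regardless of response. The missing-data sentence does not, and a strict rule would contradict the footnotes and Protocol 5.4.

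Several narrower points stand:

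- The real dispute is two combinations of nine. For N/M and M/N the body text and the proposed rule agree, and Protocol 4.1 separately discontinues subjects who achieve neither response after Re-Induction.
- The CR100 gap arises only if one observed response is enough for entry, so it cannot occur together with diversion under a single rule. *No* is also the natural level.
- Appendix D has EDC determine Maintenance eligibility automatically, so one rule is probably applied throughout. The documents do not show which. The Operations Manual was not available for this review and might settle it.
- Maintenance arms are compared among subjects randomized after routing, so no bias between them is shown.

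**Conclusion.** The inconsistency is real, and the body wording is wrong as written if the AND/OR definition is what the sponsor intends. Followed literally, it re-loads or discontinues subjects whose response was observed. It conflicts with the responder definition, the entry condition for Re-Induction and the routing in Protocol 5.4.

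The expected size is small. The number affected is not given; the illustrated range of about 2 to 19 of 265 rests wholly on assumed rates. Subjects can move into or out of ITT3, so the net effect on that population is not established. Confidence is high about the mismatch in the text. Whether any subject would actually be misrouted depends on the EDC build, which the documents do not show. The point should be corrected because it governs individual treatment and costs almost nothing to settle.

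**What to change.** Use one sentence in the Synopsis, Protocol 4.1, the Protocol Figure 1 footnote, SAP 2.2 and the SAP Figure 1 footnote. Suggested content: a component that cannot be determined counts as non-response for that component only, so missing data make a subject a non-responder only when neither component shows an observed response. Leave the separate rule on rescue and confounding medication unchanged.

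Add to Protocol 5.8 and SAP 9.1 that a missing CDAI at Maintenance entry counts as *No* for the CR100 stratum. Then confirm that the EDC and IRT specifications match.

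If the strict rule is intended, say so explicitly as an exception to AND/OR, and correct the responder rule in Protocol 4.1, both Figure 1 footnotes and Protocol 5.4.

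The cost is one aligned sentence in five places, one line on the stratum and a specification check. Visits, data collection and sample size do not change.
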